1. BACKGROUND

Over the last few decades, the incidence of End Stage Renal Disease (ESRD) has increased exponentially¹. Kidney disease significantly impacts the longevity and quality of life with survival worse than most malignant conditions. Although renal replacement therapies (RRT) like dialysis and transplantation can improve survival rates, the improvement in quality of life remains complex and difficult to assess². Renal transplantation (RT) provides the best therapy available to this cohort of patients, offering superior survival and quality of life compared to long term dialysis³.

In the lead up to the procedure, the evaluation and management of both renal transplantation donors and recipients is a multidisciplinary effort. From the early days of transplant surgery, urologists have been closely involved in all stages. The world's first successful renal transplant involved John Hartwell Harrison, a urologist who performed the donor nephrectomy in 1954⁴.

Although only 1.4-5% of ESRD is directly attributable to a urological cause, it's likely that many more patients have urological factors at play in their pathology, with multiple aspects of renal transplantation closely linked with urological knowledge and experience⁵. Urological complications such as Urinary Tract Infections (UTIs), urinary retention, ureteric anastomotic strictures, and vesicoureteral reflex (VUR) are common and can significantly impact graft function⁶. Additionally, patients have been anuric for a period prior to transplantation.

The advancements in surgical techniques, immunosuppression regimens and enhanced recovery protocols have led to a remarkable increase in success rates for both cadaveric and living donor transplantation^{7,8}. This has gradually shifted the focus towards reducing peri-operative and long-term complications what may potentially compromise graft function and patient quality of life (QoL). In this vein, a frequently underestimated but highly clinically relevant issue is bladder dysfunction or dysfunctional bladders (DB). DB can occur secondary to reduced renal function (i.e. many of these patients have been anuric for a period prior to transplantation; the impact of this bladder "disuse" is poorly understood); secondary to other causes of renal failure e.g. diabetes, hypertension; or from physical alterations in the urinary tract, which include bladder outlet obstruction, neurogenic bladder and urinary lithiasis^{9,10}.

Furthermore, life expectancy advances have led an increase to the number of older people with ESRD undergoing RT. The UK Renal Registry consistently shows a trend towards increasing median ages for patients undergoing renal transplant. The median age of renal transplantation in men in UK was 46 years and 55 years in Scotland^{1,11}. In men

> 50 years of age, Lower urinary tract symptoms (LUTS) secondary to Bladder outlet obstruction (BOO) primarily caused by Benign Prostate Hypertrophy (BPH) linearly increases with age¹². LUTS generally present as symptoms related to urinary storage (increased urinary frequency, urgency, nocturia, incontinence) or urinary voiding (poor stream, hesitancy, incomplete emptying etc.). Symptoms of these relative common conditions can be masked in patients with renal failure due to oligo-anurisis. Urodynamic studies indicate that prolonged disuse of bladder may lead to structural and functional changes including reduced bladder compliance and impaired detrusor contractility⁹. LUTS can arise after RT leading to restoration of diuresis; potentially posing a serious risk to graft function¹³.

Several researchers have advocated for investigation and treatment of bladder function before RT owing to the high prevalence of these symptoms in pre-transplant patients. However, there is a paucity of prospective data linking LUTS with post RT urological complications and significant variability in practice within the UK and Europe regarding pre-operative evaluation of patients and no clear guidance on a standardized protocol^{5,13,14}.

2. RATIONALE

The current literature is based only on a few retrospective studies, which explore the incidence and risk factors for post RT urological complications. However, none of them have investigated whether pre-existing bladder symptoms serve as a predictive marker of complications. Although some of these studies may provide an insight, they have not examined this using a longitudinal approach using standardized validated tools. There is a critical lack of research employing a prospective, longitudinal approach which employs validated tools such as International Prostate Symptoms score (IPSS) and, in particular no work in women looking at the International Consultation on Incontinence Questionnaire (ICIQ-FLUTS) for female LUTS¹⁵⁻¹⁷.

This study aims to address this gap by prospectively evaluating the prevalence and distribution of LUTS within the RT population and understand how these scores are distributed across a range of urological complications..

By stratifying patients individually by their urological risk and employing relevant screening and treatment strategies, we seek to develop a standardized pathway for pre-transplant screening which can then be utilized in a future interventional study to determine if outcomes are modifiable.

3. OBJECTIVE AND OUTCOME MEASURES/ ENDPOINTS

Primary objectives

The primary objectives are twofold:

- a. To understand the distribution of LUTS score in patients undergoing renal transplantation
- b. To describe the distribution of LUTS scores across adverse outcomes post-transplant

Secondary objectives

- Evidence of urological complications in the 6 weeks following transplantation.
- Evaluation of whether the presence of LUTS can predict graft outcomes in the 12 months following transplantation
- Whether or not pre-existing urological conditions increase the likelihood of major urological complication following transplant
- Compare patients undergoing this work-up regimen with an age/ sex matched historical cohort to determine if there is any difference in risk of post-operative urological complications with a focused pre-operative screening regimen.
- Determination of whether changing the peri-operative work-up pathway to evaluate pre-operative LUTS, will reduce the likelihood of urological complications in the year following transplant
- To assess the change in LUTS and QOL by validated tools at 6 weeks and 1 year post RT after re-establishment of diuresis.
- To assess whether duration of time on the waiting list/ presence of anuria impacts on primary outcomes and change in severity of LUTS/ QoL. Inform future end points, sample size, trial design etc. of a future interventional study
- Determination if the duration of time on the transplant waiting-list and/ or RRT vintage and/or anuria predict objective change in LUTS or adverse urological outcomes post-transplant

Primary outcome measures

LUTS will primarily be assessed using IPSS for male participants and ICIQ-FLUTS for female participants (see below), supplemented by post-void residual volume and urine flow studies.

“Urological complication” will be considered to be a composite any of the following occurring within the first 12 months following transplantation:

1. Urinary retention defined as high post-void residual volumes initiating need for indwelling catheter/ clean intermittent catheterization within the first 12 months of transplantation. (This will include patients who fail trial of void post-surgery).
2. Recurrent culture-proven urinary tract infections (≥ 2 in the first 6 months/ ≥ 3 in the first 12 months post-transplant)
3. Ureteric leak or suspected ureteric leak.
4. Deterioration in renal function (eGFR, Creatinine) due to post-renal causes:
 - Transient decline in renal function ($>20\%$ from nadir creatinine)
 - Persistent decline in renal function ($>10\%$ from nadir creatinine)
5. Sepsis of urinary source requiring hospital admission (including graft pyelonephritis)
6. Any patient undergoing any surgical or radiological intervention for a urological complication (excluding routine stent removal post-transplant) within the first 12 months of transplantation
7. Graft loss as a result to urological complications within the first year of transplantation

Secondary outcome measures

- Renal function at 12 months (eGFR, creatinine) and its association with presence and severity of pre-transplant LUTS
- Change in IPSS/ ICIQ-FLUTS scoring from baseline to 6 weeks and 1 year post RT (including QoL scores)

Table of endpoints/ outcomes

Objectives	Outcome Measures	Timepoints
Primary Objective:		
To determine the prevalence of distribution of pre-transplant LUTS	LUTS at baseline as assessed by IPSS/ ICIQ-FLUTS, flow studies and post-void residual urine volumes	Baseline
To determine the distribution of LUTS scores across adverse urological complications post-transplant	Incidence of urological complications (retention, recurrent UTIs, ureteric obstruction, need for CIC, graft pyelonephritis etc as above)	6 weeks and 12 months post-transplant
Secondary Objectives:		
To assess change in LUTS over time (includes QoL)	IPSS/ ICIQ total score and QoL sub-score, post-void residual volumes, Qmax	Baseline, 6 weeks, 12 months
To describe urological complications in patients with and without LUTS	Frequency and type of complications	6 weeks and 12 months
To correlate pre-transplant LUTS with graft function	Renal function measures (eGFR, creatinine)	6 weeks, 12 months
Impact of waiting times on outcomes	IPSS/ ICIQ total score and QoL sub-score	12 months post wait listing

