4. STUDY DESIGN

This is an observational longitudinal cohort study. Two separate patient cohorts will be considered:

1. Those approached for consent at time of transplant: baseline, 6 weeks post-transplant and 1-year post transplant measurements will be obtained
2. Those approached for consent at time of wait-listing: baseline values at time of wait-listing, time of transplant, 6 weeks and 1 year post transplant will be obtained.

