7. TRIAL PROCEDURES

This is a prospective, single center, longitudinal cohort study. Two separate patient cohorts will be considered:

3. Those approached for consent at time of transplant: baseline, 6 weeks post-transplant and 1-year post transplant measurements will be obtained
4. Those approached for consent at time of wait-listing: baseline values at time of wait-listing, time of transplant, 6 weeks and 1 year post transplant will be obtained.

Patients will be recruited over a two-year period and followed-up until they are one year post-transplant; removed from the transplant waiting list or have died.

We aim to approach all patients at the time of transplant and at the time of transplant wait-listing to offer participation.

This is primarily an observational study. History, examination and all perioperative follow-up will be conducted as would be standard of care. No additional hospital visits are required as the transplant assessment visit, transplantation, 6 week and 12 month follow-up visits will all coincide with regular clinical care.

Recruitment

Participant identification

Participants will be identified by a member of the clinical team either at time of referral for transplantation or at the time an offer of a kidney transplant offer is made. A member of the research team will be contacted and the patient screened for eligibility.

Screening

Case note review of patients' past medical and vascular access history will be undertaken by the research team to determine if eligibility criteria are met. If eligibility criteria are met, a PIS will be provided and the patient offered the opportunity to discuss the study further with the research team.

If a patient is screened but is not eligible for the trial, an anonymous record of the case will be kept in the screening log. The screening log will collect patient initials, age, and gender, date of screen failure and reason for screen failure. The screening log will be kept in the ISF.

Consent

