All patients have the right to refuse participation without giving reasons. Participants remain free to withdraw from the trial at any time without giving reasons and without prejudicing his/her further treatment. If a patient declines to consent a record of this will be made within the patient notes and in the SCOPE study screening log.

Once signed, a copy of the consent form will be given to the patient; the original kept in the local ISF and a copy placed in the patient notes. The informed consent discussion will be recorded in the participant's medical notes including the version number of the PIS provided to the participant.

Patients recruited into the trial will be assigned a unique patient identifier allowing participant to be identified i.e. 001 on all future trial documentation. An enrolment log will be maintained in the ISF to permit identification of patient names against trial numbers for those recruited to the trial. The ISF will be retained at a secure location within the Renal Transplant Unit. The enrolment log is the only place where patient identifiable information will be recorded. Upkeep and security of the ISF is the responsibility of the PI.

Interventions/ trial procedures

The interventions within this study beyond standard care are the bladder diary, IPSS/ ICIQ-FLUTS questionnaire, a bladder scan (bedside ultrasound) to measure post-void residual volume and non-invasive uroflowmetry studies. These additional interventions will be performed at time of transplant listing (where appropriate), after 1 year on the transplant waiting list (where appropriate), on the day of transplant, 6 weeks and 12 months after transplantation.

A small number of patients will not pass sufficient urine to perform flow studies/ and or urodynamics. These patients will require their bladder to be pre-filled with sterile saline prior to voiding in order to achieve an accurate reading. A protocol for how to undertake this is outlined in Appendix 1 and would be performed by the ward doctor as part of clinical care. The rates of bladder filling and urodynamic studies being performed within trial will be monitored by the Trial Steering Committee at 3- 6 monthly intervals to ensure that these are clinically appropriate.

Study visits

A schedule of study visits is outlined below. All study visits will correspond to pre-existing clinical visits.

For patients recruited on day of transplant:

Study assessments	Visits			

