8 STATISTICS AND DATA ANALYSIS

Sample size

This is a non-interventional, exploratory study, the results of which we hope will may inform a future interventional study. The primary aims are two-fold:

- a. To understand the distribution of LUTS score in patients undergoing renal transplantation
- b. To describe the distribution of LUTS scores across adverse outcomes post-transplant

Our sample size has been chosen based on three factors:

1. Feasibility within the anticipated timescale
2. The likelihood of obtaining a representative distribution of LUTS scores assuming a relatively normal distribution from other feasibility studies
3. The existing literature (it'll be the largest observational study of evaluating LUTS in transplant patients, and the only one to evaluate longitudinally)

We aim to recruit 100 patients into each of the two parts of the study over two years.

The Glasgow Renal Transplant Unit performs 100-150 renal transplants annually and assesses over 200 patients per year. Conservatively, over a two year period, 100 patients could be recruited by approaching and consenting less than half of those transplanted and fewer than 25% of those assessed for transplantation.

We anticipate a 5-10% death rate (as would be standard in the transplant population). We do not anticipate that patients will be lost to follow-up as they all come back to regular post-transplant clinics, but assuming 5-10% withdraw or have incomplete data sets that should still leave a minimum of 40 men and 40 women with complete datasets for evaluation.

There is little data on the prevalence or distribution of LUTS in the renal transplant population in men¹⁵⁻¹⁷, and no data in women. Based on the previous two year's data from our own center we anticipate that between 50-60% of patients will have one of the composite urological complication outcomes. (We have deliberately chosen a broad definition of "urological complications", with high prevalence, for this initial study so that

all possible relevant outcomes are considered so that all relevant outcomes are considered and recorded. This could be refined for future interventional studies to be more specific if deemed appropriate.)

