Recording results: The pre- and post-void bladder scan results and trace from the flow dynamics study should be included within the *nursing notes* (so that the trace can be scanned into the clinical portal)

Abnormal/ equivocal findings:

For equivocal bedside tests carried out on the day of transplantation, the operating surgeon should be informed of any equivocal results, but transplantation should proceed as anticipated with view to early post-operative Urology referral for consideration of Urodynamics.

For equivocal bed side tests carried out in pre-assessment clinic, transplant listing should be delayed until satisfactory Urology opinion has been obtained after due investigations.

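### The secondary objective of determining that the new work-up will reduce complications cannot be met by an observational cohort set against an age- and sex-matched historical group

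*Protocol*

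**What the plan says.** The objective appears in the Scientific Summary (under both objectives and secondary outcomes) and again in Protocol section 3: "Determination of whether changing the peri-operative work-up pathway to evaluate pre-operative LUTS, will reduce the likelihood of urological complications in the year following transplant". The contrast offered to answer it is listed just before it: "Compare patients undergoing this work-up regimen with an age/ sex matched historical cohort to determine if there is any difference in risk" of post-operative complications.

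Section 4 describes the design: "This is an observational longitudinal cohort study". There is no concurrent comparison group and no allocation. Section 2 says that the screening pathway would be taken into a future interventional study to learn whether outcomes are modifiable. The Plain English Summary adds that the team does not yet know what to measure or how best to intervene.

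On measurement, section 7 (Interventions/trial procedures) lists what goes beyond usual care: a bladder diary, a symptom questionnaire, "a bladder scan (bedside ultrasound) to measure post-void residual volume and non-invasive uroflowmetry studies". These are repeated at 6 weeks and 12 months after transplant. Section 9 (Assessment and management of risk) says that no investigations beyond standard care are anticipated.

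For equivocal tests on the day of transplant, Appendix 1 says that "transplantation should proceed as anticipated with view to early post-operative Urology referral".

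**The concern.** The wording is causal, and the design cannot carry it. Three things other than the work-up can separate the study cohort from past patients.

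- **Selection.** Study patients consented, are first-time recipients and have no reconstructed bladder. The protocol names only age and sex as matching factors.
- **Calendar time.** The two groups are treated in different periods.
- **Detection.** Study patients have extra residual-volume and flow tests inside the 12-month outcome window. One component of the composite is retention shown by high residual volume that leads to catheterisation. Another is any urological intervention, which can follow from such a finding.

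Detection pushes towards more complications in the study group, while selection and calendar time can push either way. Neither a fall nor a rise could be credited to the work-up. The Scientific Summary expects the results to affect patient care directly, so a biased answer in either direction could mislead the design of the pathway.

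**Working it through.** **1. The passages side by side.** Section 3 sets out to determine that a change of pathway lowers risk. Section 4 gives an observational cohort. Section 2 reserves the question of modifiability for a later interventional study. The objective and the rationale cannot both stand as written. The endpoint table in section 3 and the analysis list in section 8 contain no historical comparison, so nothing else in the protocol narrows the objective.

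**2. The protocol's own figure.** Section 8 recruits 100 per part, allows 5–10% deaths and 5–10% withdrawal or incomplete data, and expects at least 40 men and 40 women. At the upper rates, 100 × (1 − 0.10 − 0.10) = 80, or 100 × 0.90 × 0.90 = 81. The 80 reproduces; the 40/40 split also needs equal numbers of each sex.

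**3. Comparator rate.** Section 8 states: "Based on the previous two year's data from our own center we anticipate that between 50-60% of patients will have one of the composite" urological outcomes. I take the midpoint, 55%, as the historical rate. That is an assumption, because the protocol does not say which years the historical cohort covers.

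**4. Detection with no true effect.** Let s be the share of the events found by study follow-up that historical records also hold. The protocol does not give s; I assume 0.80 to 0.95. The rate seen in the study cohort is then 0.55 / s.

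| s | Study rate | Spurious excess |
|---|---|---|
| 0.95 | 57.9% | 2.9 points |
| 0.90 | 61.1% | 6.1 points |
| 0.85 | 64.7% | 9.7 points |
| 0.80 | 68.75% | 13.75 points |

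Across historical rates of 50–60% the excess runs from 2.6 points (0.50/0.95 − 0.50) to 15.0 points (0.60/0.80 − 0.60). A true relative reduction of 1 − s, that is 5–20%, would be wholly hidden. This applies s to the whole composite. The mechanism mainly reaches retention and the interventions that follow from it, so the lower values of s are the harder to reach.

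**5. Confounding with no true effect.** Take an unmatched factor with risk ratio R, present in 20% of study patients and 40% of historical patients (all assumed). The study rate is 0.55 × [1 + 0.2(R − 1)] / [1 + 0.4(R − 1)].
- R = 1.5: 0.55 × 1.10 / 1.20 = 50.4%.
- R = 2: 0.55 × 1.20 / 1.40 = 47.1%.

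That is an apparent fall of 5 to 8 points. With the prevalences reversed it would be a rise.

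**6. Precision, for illustration only.** Assume 80 per group, 1:1 matching, two-sided 5% and 80% power. For 55% against 33.2% (difference 0.218, mean rate 0.441):
- standard error under no difference: √(2 × 0.441 × 0.559 / 80) = 0.0785;
- standard error under the difference: √[(0.55 × 0.45 + 0.332 × 0.668) / 80] = 0.0766;
- (0.218 − 1.96 × 0.0785) / 0.0766 = 0.84, which is 80% power.

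The detectable fall is thus about 22 points, and power for a 10-point fall is about 24%. With 200 historical controls the detectable fall is 18.4 points (80 v 200). With both parts pooled it is 14.8 points (160 v 200).

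**The case against.** **The study is exploratory and the objective is secondary.** Section 8 calls the analysis exploratory, and section 2 already defers modifiability. This is fair, and it limits the consequence. It is also the reason to use descriptive wording, since an exploratory study should not list a determination of effect.

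**A reader might infer that historical outcomes are known to be ascertained less intensively.** The documents do not say so. Section 7 also states: "History, examination and all perioperative follow-up will be conducted as would be standard of care", at visits that coincide with regular care. The 50–60% figure suggests that the composite can be drawn from past records. Retention counts only when it leads to catheterisation, and it includes failed trials of voiding; these are clinical events. What stands is narrower: extra scans inside the outcome window can prompt catheterisation that would otherwise not have happened or been recorded. The statement in section 9 that no extra investigations are expected contradicts section 7, and the two must be reconciled.

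**A reader might infer that Part 1 tests no change of pathway.** Appendix 1 does not support that. An equivocal result on the day is passed to the surgeon and may lead to early urology referral, which falls within the 12 months. Part 1 leaves little room to change care before the operation, but some room after it.

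**The historical cohort may well have the same exclusions.** The protocol is silent, and detailed selection and adjustment may sit in an analysis plan that is not shown. The protocol does fix the matching factors as age and sex, and it fixes the causal objective. Those two are open to criticism here.

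**Conclusion.** The point holds for the objective as worded: an observational cohort compared with an age- and sex-matched historical group cannot determine that the work-up reduces complications, and section 2 says as much. This needs no assumption.

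The likely detection difference is an inference from sections 3 and 7. It mainly affects retention and resulting interventions, and its size is unknown. Under the assumed 80–95% capture it would be about 3 to 14 points at a 55% rate, which a larger sample would not remove. Confounding of similar size could act the other way.

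A reader might also take the 22-point detectable fall as a sample-size error. It is not one. The protocol states no power for this comparison, the 1:1 matching and the 80 controls are assumptions, and the figure shrinks with more controls or pooled parts.

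**What to change.** - Delete the objective about reducing complications, or restate it as a descriptive, hypothesis-generating comparison from which no causal conclusion will be drawn, in line with section 2. Change the Scientific Summary and section 3 together.
- Apply the study's eligibility criteria to the historical cohort and state the years it covers.
- Use the same record-based outcome definitions in both periods. Exclude events prompted only by study tests, or show them separately.
- Report Part 1 and Part 2 separately. Part 1 testing, on the day of transplant or the day before, acts mainly through post-operative referral. Part 2 testing starts before or at listing, and Appendix 1 delays listing after an equivocal clinic result, so those who reach transplant are a differently selected group.
- Adjust for donor type, RRT vintage and diabetes, already collected in the study cohort, and report the difference with a 95% confidence interval.
- Reconcile sections 7 and 9 on whether the scans and flow tests are additional to standard care.

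The cost is one claimed objective and a slightly more restricted record extraction, which must also capture the three adjustment factors for past patients. Visits, recruitment and the primary objectives do not change.

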It is anticipated that results will directly impact patient care and help stratify patients before transplantation. This will allow us to implement bladder optimizing protocols to maximize post-transplant graft function.

The results will be presented at international platforms and will be published in high-impact medical journals, which will help fill a lacuna in the literature. This may pave way for a future multicenter interventional study.

ABBREVIATIONS

PLAIN ENGLISH SUMMARY

Many patients with kidney failure need a kidney transplant. Some of these patients will have problems relating to the storage or passage of urine. In many cases this is unrecognized before transplant, especially if the patient no longer passes urine. This can lead to problems after the transplant, resulting in infections, complications and poor kidney function.

There are very few studies which have looked at how issues with the patient's urinary tract and bladder affect the outcome of kidney transplant. However, it's well-recognized amongst kidney transplant surgeons to be a significant problem. This study aims to determine the number of patients who have undiagnosed waterworks issues before transplant and investigate if these issues make it more likely for the patient to have urinary tract infections, poor kidney transplant function or other complications in the year following transplant.

We will approach everyone having a kidney transplant in Glasgow within a two-year period: both when they join the transplant waiting list and when they receive a transplant. We will follow patients up at 6 weeks and 1 year after transplant, taking measures of bladder function from history, questionnaires and simple studies of urine flow/ bladder function. We hope to recruit 100 patients over in each group over a two year period.

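### LUTS severity is graded by questionnaire alone even in patients who pass no urine, so masked symptoms can be classed as low LUTS and the return of urine can read as worsening

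*Protocol*

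**What the plan says.** **Measure and grade.** Protocol section 3 (Primary outcome measures) states "LUTS will primarily be assessed using IPSS for male participants and ICIQ-FLUTS for female participants"; post-void residual and flow studies supplement them. Section 7 (IPSS/ICIQ-FLUTS) sets severity from the scores only. Men above 7 on the IPSS are moderate to severe. Women are mild at 0-11, moderate at 12-23 and severe from 24.

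**Who is covered.** Section 6 does not exclude anuric patients, and the visit tables in section 7 schedule the questionnaire at every assessment. No rule says how to grade someone who does not void.

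**Masking is acknowledged.** The Background says "Symptoms of these relative common conditions can be masked in patients with renal failure due to oligo-anurisis". The Plain English Summary says of bladder problems: "In many cases this is unrecognized before transplant, especially if the patient no longer passes urine". The Background adds that "LUTS can arise after RT leading to restoration of diuresis".

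**Provision for low output.** Section 7 and Appendix 1 fill the bladder so that flow and residual volume can be measured. Native urinary output is recorded in the urological history.

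**Outcomes that use the score.** These are the baseline distribution (primary objective a), the distribution across complications (primary objective b), and change in score from baseline to 6 weeks and 1 year. Section 3 also plans to examine anuria as a predictor of LUTS change and of adverse outcomes.

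**The concern.** The protocol recognises that low urine output makes the objective tests unreliable and corrects for it. It recognises the same problem for symptoms but leaves the primary measure uncorrected. A patient who passes no urine has little opportunity to report poor stream, hesitancy or frequency, so a low score may reflect absent urine rather than a healthy bladder.

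Three results are exposed. Moderate-severe prevalence may be understated. The change score may mix unmasking with true deterioration. The comparison of anuric with other patients on LUTS change may be decided partly by how the baseline is measured. Section 8 wants these distributions to inform the endpoints and sample size of a later interventional trial, so a distortion here would carry forward.

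**Working it through.** **The plan's own figure.** From 100 recruited, with 10% deaths and 10% withdrawn or incomplete: 100 × (1 − 0.10 − 0.10) = 80, or 100 × 0.9 × 0.9 = 81. At an equal sex split this is 40 men and 40 women, as section 8 states. That figure stands. The protocol gives no figure for the low-output share, so everything below is illustrative.

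**Assumptions (not in the documents).** Among voiders, half have moderate-severe LUTS, with complication risk 65% against 45% in the rest, a 20-point difference. A share *a* of the cohort has low output, all of them score low, and their complication risk is *r*. Complete masking is the extreme case.

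**1. Prevalence.** Observed moderate-severe prevalence = 0.50 × (1 − *a*), which is 45%, 40% and 35% at *a* = 10%, 20% and 30%. If a fraction *q* of the low-output group truly has moderate-severe dysfunction, the shortfall is *a* × *q*. With *q* = 50%, the true figure is 50% throughout.

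**2. Complication contrast.** Low-output patients join the reference group with weight *w* = *a* / [0.5(1 − *a*) + *a*]. The observed difference in points is 20 − *w* × (*r* − 45).

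| *a* | *w* | *r* = 45% | *r* = 55% | *r* = 65% | *r* = 75% |
|---|---|---|---|---|---|
| 10% | 0.10/0.55 = 0.182 | 20.0 | 18.2 | 16.4 | 14.5 |
| 20% | 0.20/0.60 = 0.333 | 20.0 | 16.7 | 13.3 | 10.0 |
| 30% | 0.30/0.65 = 0.462 | 20.0 | 15.4 | 10.8 | 6.2 |

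The sign depends on *r*. At 45% there is no dilution. Below it the contrast widens: *r* = 35% and *a* = 20% gives 20 + 0.333 × 10 = 23.3. The overall complication rate, 0.55(1 − *a*) + *a* × *r*, runs from 52% to 61% across the table. Only the bottom-right cell leaves the 50-60% that section 8 expects.

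A milder set of assumptions gives less. Suppose 40% truly have moderate-severe LUTS, risks are 70% and 45%, and low-output patients have the same mix and risks as voiders. The reference risk is then [0.6 × 0.45 + 0.4*a* × 0.70] / (0.6 + 0.4*a*), and the 25-point difference falls to 24.2, 23.4, 22.1 and 20.8 at *a* = 5%, 10%, 20% and 30%.

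**3. Change from baseline.** Suppose a man's underlying score is a stable 8, just above the cut-off, but reads 0 while he is anuric. The mean among men then shows a false worsening of 8 × *a*: 0.8, 1.6 and 2.4 points at 10%, 20% and 30%. Under the first set of assumptions with *q* = 50%, the number moving from low to moderate-severe with no change in the bladder is 80 × 0.5 × *a* = 4, 8 and 12 of 80.

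**4. Anuria as a predictor.** In the same example, anuric men change by 8 and voiders by 0. Anuria 'predicts' an 8-point worsening although nothing in the bladder has changed. That is the circular part.

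**The case against.** **The protocol does attend to anuria.** It plans to relate anuria to LUTS change, lists flow and residual volume beside the questionnaires in the endpoint table, and records native output. An analysis plan that is not shown could add displays by urine output. This stands as mitigation. It does not alter the grade, which the protocol itself fixes, and no rule lets a filled-bladder result override it.

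**A low score may be an accurate record.** Section 3 sets out to assess change once diuresis returns, so symptoms appearing then are partly the target. This also stands. The difficulty is that, unstratified, unmasking and new onset cannot be told apart.

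**Stronger readings that the documents do not support:**
- *All low-output patients score near zero.* The text says only that symptoms can be masked. Oliguric patients still void and can report symptoms.
- *All of them are graded mild.* That is literal only for women; men merely fail to exceed 7.
- *The association is bound to be diluted.* That requires a risk in low-output patients above that of low-LUTS voiders, which is not stated. Section 8 also leaves the association analysis optional.
- *The sample size fails because of the floor.* The phrase "assuming a relatively normal distribution from other feasibility studies" belongs to one of three reasons given, and no calculation uses it.
- *The protocol contradicts itself on numbers.* The Background's "many of these patients have been anuric for a period prior to transplantation" concerns anuria at some time. Section 7's "A small number of patients will not pass sufficient urine to perform flow studies/ and or urodynamics" concerns who needs filling for a test. Both are loose, but they can both be true.
- *Scores should be reported in voiders only.* That would narrow primary objective (a), which covers everyone undergoing transplantation.

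**Conclusion.** The point holds as a defect in how the grade and the change score are defined. Following the protocol as written puts anuric patients with masked symptoms among the low scorers, can understate moderate-severe prevalence, lets return of urine count as worsening, and makes the anuria-change analysis partly circular.

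The direction for prevalence and change follows from the protocol's own account of masking; the size does not. Under the assumptions shown, prevalence reads 45% down to 35% against 50% among voiders, and the complication contrast reads anywhere from an undiluted 20 points down to 6. These effects shrink if masking is incomplete or the low-output share is below 10%. No figure in the protocol is refuted. The change is worth making before recruitment, though the exploratory design limits its weight.

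**What to change.** **Stratum.** Pre-define a low-output stratum for analysis, using the native urinary output already collected and the daily-output limit in Appendix 1 (anuric, or under 250 ml per day), with anuric patients identified separately. This is an analysis definition only and does not touch who has the bladder filled.

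**Grading.** Class anuric patients as not gradable by questionnaire. Keep oliguric patients' scores, but show them separately.

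**Reporting.** Keep the whole-cohort score distribution for objective (a). Also report scores, severity prevalence, change from baseline and any LUTS-complication analysis by stratum. Describe the low-output stratum mainly by filled-bladder residual volume and Qmax and by its own complication rate. Summarise scores by median and interquartile range. Report the low-output share, which is itself useful for planning the later trial.

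**Cost.** Wording only, with no new data. Strata will be small: of 80 complete datasets, a share of 10%, 20% or 30% leaves 72, 64 or 56 voiders (36, 32 or 28 per sex at an equal split) and 8, 16 or 24 low-output patients. The stratified results are therefore descriptive.
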